#### **6.4. Subject Withdrawal**

Subjects may withdraw from the study at any time at their own request, or they may be withdrawn at any time at the discretion of the investigator or sponsor for safety or behavioral reasons, or the inability of the subject to comply with the protocol-required schedule of study visits or procedures at a given study site.

If a subject does not return for a scheduled visit, every effort should be made to contact the subject. If a subject is lost to follow-up, the enrolling physician (or designee) will attempt to contact the alternate contact.

In any circumstance, every effort should be made to document subject outcome, if possible. The investigator should inquire about the reason for withdrawal, request the subject to return all unused investigational product(s), request the subject to return for a final visit, if applicable, and follow up with the subject regarding any unresolved adverse events (AEs).

If the subject withdraws from the study, and also withdraws consent for disclosure of future information, no further evaluations should be performed, and no additional data should be collected. The sponsor may retain and continue to use any data collected before such withdrawal of consent.

A subject who is withdrawn from the study is expected to be subsequently managed by their physician according to their usual practice. See also [Section 6.7](#).

#### **6.5. Guidelines for Image Guidance (eg, TEE/TOE or CT) Suggesting Atrial Thrombus**

The investigator should follow their usual practice, and in accordance with local and national guidelines. Positive TEE/TOE or CT will be submitted for adjudication.

It is expected that in the event of imaging suggesting atrial thrombus, that any cardioversion attempt would be deferred for a minimum period of at least 3 weeks of further anticoagulation, consistent with local/national guidelines. It would also be expected that repeat imaging would take place prior to consideration of further cardioversion attempts.

## 6.6. Guidelines for Bleeding/Suspected Bleeding

For subjects with clinically significant bleeding, the anticoagulant should be discontinued. Bleeding should be managed according to local standard of care and may include measures such as surgical haemostasis, volume resuscitation, and transfusion of blood products as deemed appropriate and in keeping with the treating physician's clinical judgment.

There is no specific antidote to reduce apixaban activity. Investigators should refer to the local prescribing information for further advice on significant bleeding that may occur on apixaban.

## 6.7. Treatment Transition Guidelines

At the end of the study or upon subject withdrawal it is expected that subsequent management and treatment for the subject will be conducted by their physician according to their usual practice and preferred treatment.

If switching anticoagulation treatment is required, then this will be managed in accordance with the local label.

For example, the USPI states *“Switching from warfarin to ELIQUIS: Warfarin should be discontinued and ELIQUIS started when the international normalized ratio (INR) is below 2.0”, “Switching from ELIQUIS to warfarin: ELIQUIS affects INR, so that INR measurements during coadministration with warfarin may not be useful for determining the appropriate dose of warfarin. If continuous anticoagulation is necessary, discontinue ELIQUIS and begin both a parenteral anticoagulant and warfarin at the time the next dose of ELIQUIS would have been taken, discontinuing the parenteral anticoagulant when INR reaches an acceptable range” and “Switching between ELIQUIS and anticoagulants other than warfarin: Discontinue one being taken and begin the other at the next scheduled dose”.*

The SmPC states *“Switching from Vitamin K antagonist (VKA) therapy to Elixquis: When converting patients from Vitamin K antagonist (VKA) therapy to Elixquis, discontinue warfarin or other VKA therapy and start Elixquis when the international normalized ratio (INR) is < 2.0” and “Switching from Elixquis to VKA therapy: When converting patients from Elixquis to VKA therapy, continue administration of Elixquis for at least 2 days after beginning VKA therapy. After 2 days of coadministration of Elixquis with VKA therapy, obtain an INR prior to the next scheduled dose of Elixquis. Continue coadministration of Elixquis and VKA therapy until the INR is ≥ 2.0”*

For other countries, the local approved label should be referred to for advice.

## 7. ASSESSMENTS

Every effort should be made to ensure that the protocol-required tests and procedures are completed as described. However, it is anticipated that from time to time there may be circumstances outside of the control of the investigator that may make it unfeasible to perform the test. In these cases the investigator will take all steps necessary to ensure the safety and well-being of the subject. When a protocol-required test cannot be performed, the investigator will document as soon as possible the reason for this and any corrective and

preventive actions which he/she has taken to ensure that normal processes are adhered to. The study team will be informed of these incidents in a timely fashion.

### **7.1. Demography**

Age, gender and race will be captured within the CRF at Visit 1.

### **7.2. Medical History**

Pertinent AF and other relevant medical history will be captured within the CRF at Visit 1. It is expected that subjects will have routine work-up at presentation according to the investigator's usual practice, with a minimum expectation of ECG confirmation of AF diagnosis. At Visit 1, an ECG to confirm AF does not need to be repeated for the protocol, if it was taken on the day prior to, or the same day as Visit 1.

### **7.3. CHA2DS2-VASc Score**

The CHA2DS2-VASc (congestive heart failure, hypertension, age, diabetes, stroke, vascular disease, age, sex category) stroke risk score assigns 2 points age over 75 years and for a history of stroke or transient ischemic attack (TIA), and 1 point each for recent congestive heart failure, a history of hypertension, diabetes, vascular disease, age 65-74 years or sex category (ie, female gender). The summed score quantifies the risk of stroke in subjects with AF.

The CHA2DS2-VASc score will be assessed and the category scores will be captured within the CRF at Visit 1.

### **7.4. Clinical Endpoints**

Clinical endpoints will be assessed by the Investigator to determine whether they meet the protocol criteria as described below. Clinical events meeting the criteria will be recorded on the CRF and independently adjudicated.

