### **3. STUDY DESIGN**

This is a randomized, active controlled, parallel-group, open label study.

[figure not shown]
Approximately 1500 subjects will be randomized 1:1 to apixaban or usual care (parenteral heparin and/or oral anticoagulation with Vitamin K antagonist (excluding other NOACs)). Usual care will be administered as per local practice and/or approved label.

Apixaban or usual care (parenteral heparin and/or oral anticoagulation with Vitamin K antagonist (excluding other novel oral anticoagulants (NOACs))) will be administered from randomization up to 30 days following cardioversion or 90 days post randomization if cardioversion is not performed within that timeframe.

[figure not shown]
Following randomization, clinical endpoints, cardioversion details (timing, type, attempts, and rhythm status), length of in-patient hospital stay and use of image guidance will be collected during the 30 days following the cardioversion or during the 90 days post randomization if cardioversion is not performed.

A schematic diagram below (Figure 1) shows the design of the study:

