## **7.7. Collection of Local Clinical Laboratory Parameters**

Local clinical laboratory assessments should be performed as part of the routine care for subjects undergoing cardioversion at the clinical practice.

From these routine assessments hemoglobin and serum creatinine will be recorded within the CRF from Visit 1 to Visit 3.

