#### **9.4. Independent Adjudication**

Independent Adjudicator(s) will review and adjudicate all clinical endpoints and positive TEE/TOE or CT without awareness of treatment allocation, ie, in a blinded manner. The responsibilities and procedures followed are described in the Adjudication Charter.

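### As the protocol and SAP are written, blinded adjudication receives only events that the unblinded investigator has already judged to qualify, so it cannot recover events under-referred in one arm

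*Protocol*

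**What the plan says.** Protocol 3 sets the design: "This is a randomized, active controlled, parallel-group, open label study". Protocol 7.4 then gives two steps. First, "Clinical endpoints will be assessed by the Investigator to determine whether they meet the protocol criteria". Second, "Clinical events meeting the criteria will be recorded on the CRF and independently adjudicated".

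Protocol 9.4 describes the adjudication: "Independent Adjudicator(s) will review and adjudicate all clinical endpoints and positive TEE/TOE or CT without awareness of treatment allocation". It leaves the detail elsewhere: "The responsibilities and procedures followed are described in the Adjudication Charter". Imaging follows the same one-way pattern in Protocol 6.5: "Positive TEE/TOE or CT will be submitted for adjudication".

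Other data that could reveal a missed event are collected. Protocol 8.1.1 requires all serious adverse events, and 8.2.1 requires all identified nonserious ones. Under Protocol 7.7, "hemoglobin and serum creatinine will be recorded within the CRF from Visit 1 to Visit 3". SAP 8.2.5 puts those laboratory values in listings only.

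SAP 5 and 8.2.4 base the analyses of stroke, systemic embolism, death and both bleeding endpoints on adjudicated events. The one planned comparison of investigator and adjudicator (SAP 8.2.5) covers TEEs, with the arms pooled.

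**The concern.** Adjudication blinded to treatment guards against a judgement of events coloured by knowledge of the drug. It does so fully only if the set of events it receives was not itself selected with that knowledge. Under 7.4 the selection comes first and is made by someone who knows the arm. An event wrongly referred can be struck out. An event wrongly held back is not seen.

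The room for judgement differs by endpoint:

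- **Clinically relevant non-major bleeding (7.4.4)** ends in catch-all items: clinical consequences, unplanned contact with a physician, a temporary stop of study drug, or interference with daily life. Some depend on decisions taken by people who know which drug the patient is on.
- **Major bleeding (7.4.3), systemic embolism (7.4.2) and stroke (7.4.1)** have harder criteria, but someone must still recognise and classify the event.
- **All-cause death** needs no judgement against criteria.

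The study is descriptive, so no type I error rate is at stake. What is at stake is the estimates: the SAP still reports hazard ratios with confidence intervals and p-values (8.1.2), and risk ratios with p-values comparing the arms (8.2.4).

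**Working it through.** **1. Is there another route to adjudication?** Taking the relevant sections in turn:

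- Protocol 7.4: events that the investigator judges to meet the criteria. Suspected but rejected events are not mentioned.
- Protocol 9.4: all clinical endpoints and positive images. What counts as a recorded endpoint is settled by 7.4, so this adds no route.
- Protocol 2: links serious adverse events handled as endpoints to the adjudication committee and the DMC, but describes no screening for missed ones.
- Protocol 8.1.1 and 8.2.1: adverse events are collected, with no stated link to adjudication.
- SAP 8.2.5: compares investigator and adjudicator for adjudicated TEEs only, and not by arm.

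No route is stated. The Charter could supply one.

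**2. The plan's own figures (Protocol 9.1).** Stroke and systemic embolism: (1 + 3)/1500 = 0.27%, given as about 0.3%. Major bleeding: (2 + 5)/1500 = 0.47%, given as about 0.45% (0.0045 × 1500 = 6.75, about 7 events). Both reproduce. No prediction is given for clinically relevant non-major bleeding, so the effect on that endpoint cannot be put in events.

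**3. Effect on the risk ratio.** Let s_A and s_U be the probabilities that a true event is referred on apixaban and on usual care. Suppose that adjudicators classify every referred event correctly. Then

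observed RR = true RR × s_A / s_U.

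The documents give no referral probabilities; those below are assumptions. With a true RR of 1:

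| s_A | s_U | Observed RR |
|---|---|---|
| 0.80 | 0.95 | 0.84 |
| 0.90 | 0.75 | 1.20 |
| 0.90 | 0.90 | 1.00 |
| 0.70 | 1.00 | 0.70 |
| 1.00 | 0.80 | 1.25 |

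Over s_A from 0.7 to 1.0 and s_U from 0.8 to 1.0, the factor runs from 0.70 to 1.25. Equal under-referral leaves the ratio unbiased, though it lowers both event rates.

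**4. Effect at the predicted counts.** One event is 1/4 = 25% of the predicted stroke and embolism total and 1/7 = 14% of the predicted major bleeds. With 750 per arm, the predicted 2 against 5 major bleeds give RR 0.40. One further apixaban bleed gives 3 against 5, RR 0.60. One fewer on usual care gives 2 against 4, RR 0.50. If 10% to 30% of true events are not referred (assumed), the chance of losing at least one of five is 1 − 0.9⁵ = 41% to 1 − 0.7⁵ = 83%.

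**5. Against sampling error.** The exact 95% intervals for 2/750 and 5/750 are 0.03% to 0.96% and 0.22% to 1.55%. An approximate 95% interval for the RR uses the standard error of its logarithm, √(1/2 + 1/5 − 2/750) = 0.835, giving 0.4 × exp(±1.96 × 0.835), or 0.08 to 2.06. For major bleeding, chance variation is far larger than a factor of 0.84.

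**The case against.** The strongest answer is that the referral procedure belongs in the Adjudication Charter, to which 9.4 points. It may already require suspected events or trigger terms to be sent. The documents neither state nor exclude this. A reader might infer that adjudication in this trial certainly has no access to missed events; the documents support only that the protocol and SAP state no such access. This limit stands.

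A reader might also infer that under-referral took place, or that it favours apixaban. Nothing in the documents shows either. The referral rates above are assumptions, and the two main examples point in opposite directions.

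It would be too strong to call all the bleeding criteria subjective. Hematoma size in 7.4.4 is a numeric threshold, and the major-bleeding criteria are largely objective once bleeding is overt. The catch-all items are also broad, which may encourage over-referral, and adjudication can correct that. This is why the exposure is ranked by endpoint.

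Finally, the study is descriptive, its intervals will be wide, and a bleed recorded as an adverse event but not referred still appears in the safety tables by arm. That limits the consequence. It does not remove it: such a bleed is absent from the adjudicated counts on which the between-arm ratios rest, and a wide interval makes no allowance for a systematic shift.

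**Conclusion.** The point holds for the protocol and SAP as written. The stated rule makes blinded adjudication one-sided: it can lower the count of referred events but cannot add to it. As written, the plan could neither detect nor correct a difference in referral between arms.

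The size and direction of any bias are unknown. Under the assumed referral rates, a true risk ratio of 1 would be reported between 0.70 and 1.25. Equal referral in both arms gives no bias in the ratio. These figures assume correct adjudication of whatever is referred. The conclusion about the route depends on the Charter: if it already provides triggers, what remains is to bring 7.4 into line with it. The change should be made because it is cheap, not because bias has been shown.

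**What to change.** 1. Check the Adjudication Charter for a suspected-event or trigger route, and align Protocol 7.4 with it.
2. In 7.4, require referral of all suspected stroke, systemic embolism and bleeding events, whatever the investigator's own classification. Deaths need no such change, since every death already counts.
3. Before database lock, have staff blinded to arm search the adverse-event and serious-adverse-event terms for bleeding, stroke or TIA, and embolism. Add a hemoglobin fall of 2 g/dL or more between visits as a trigger for review only, because 7.4.3 also requires clinically overt bleeding.
4. Send unreferred hits to the existing adjudicators.
5. In the SAP, report referred and confirmed counts by arm for each endpoint.

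The search starts from data already collected and needs no new visits. The cost is some extra adjudication packages and requests to sites for source documents such as notes, imaging and transfusion records. Two limits remain. Suspicion is still a judgement made with knowledge of the arm, so step 2 lowers the filter without removing it. The search also cannot recover an event never recorded as an adverse event, unless a hemoglobin fall reveals it.

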#### **7.4.1. Acute Stroke**

An acute stroke is defined as a new, focal neurological deficit of sudden onset, lasting at least 24 hours, that is not due to a readily identifiable non-vascular cause (ie, brain tumor, trauma). All strokes during the study will be assessed and classified as primary hemorrhagic, non-hemorrhagic, infarction with hemorrhagic conversion, or unknown, as defined by the American College of Cardiology (ACC):

- **Primary hemorrhagic:** a stroke with documentation on imaging [eg, computed tomographic (CT) scan or magnetic resonance imaging (MRI)] of hemorrhage in the cerebral parenchyma, or a subdural or subarachnoid hemorrhage. Evidence of hemorrhagic stroke obtained from lumbar puncture, neurosurgery, or autopsy can also confirm the diagnosis.
- **Non-hemorrhagic:** a focal neurological deficit that results from a thrombus or embolus (and not due to hemorrhage) that appears and is still partially evident at 24 hours.

- Infarction with hemorrhagic conversion: no evidence of hemorrhage on an initial scan but appeared on a subsequent scan.
- Unknown type/no imaging performed: the type of stroke could not be determined by imaging or other means (lumbar puncture, neurosurgery).

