#### **7.4.3. Major Bleeding**

Clinically overt bleeding is defined as new onset, visible bleeding or signs or symptoms suggestive of bleeding with confirmatory imaging techniques which can detect the presence of blood (eg, ultrasound (US), CT, MRI).

The definition of major bleeding described below is adapted from the International Society on Thrombosis and Hemostasis (ISTH) definition.

Major bleeding is defined as clinically overt bleeding that is accompanied by one or more of the following:

- A decrease in hemoglobin (Hgb) of 2 g/dL or more
- A transfusion of 2 or more units of packed red blood cells
- Bleeding that occurs in at least one of the following critical sites:
  - Intracranial.
  - Intra-spinal.
  - Intraocular (within the corpus of the eye; thus, a conjunctival bleed is not an intraocular bleed).
  - Pericardial.
  - Intra-articular.
  - Intramuscular with compartment syndrome.
  - Retroperitoneal.
- Bleeding that is fatal.

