- age (< 65 years old, ≥ 65 years old)
- gender.
- For the clinical endpoints (stroke/embolism/death), also analyze by (first) cardioversion status: ‘Interventional cardioversion’, no cardioversion, or ‘Spontaneous cardioversion’
- For clinical endpoints, breakdown summaries by Apixaban initial dose levels (loading dose vs. no loading dose) will be produced.

We will display graphically the Kaplan-Meier product-limit estimators of the time to

- Composite of first adjudicated stroke or systemic embolism,
- First Major bleeding event,
- Composite of first major bleeding and clinically relevant non-major bleeding
- All cause death.

8.2.5. Other analyses:

The full analysis set will be used to summarize data on cardioversion details, length of in-hospital stay and usage of image guidance.

- Cardioversion details will be summarized by number of attempts (a separate table will be presented for each number of attempts).
 - The summary for first attempt will be based on the full analysis set. Timing of cardioversion will be the time from randomization to the first attempt only, with time to first attempt censored at the last day of follow-up if an attempt has not been made.
 - The hazards ratio (and p-value) will be calculated for time from randomization to the first attempt at cardioversion, comparing image guided to non-image guided subjects.
 - The second attempt will be summarized based on the subset of the full analysis set that already had the first cardioversion, etc.

- For each attempt we will summarize the number and proportion of subjects with cardioversion attempts and the number and proportion with each rhythm status.
 - Demog/baseline tables will be subset for 1) subjects with no cardioversion attempt, 2) subjects with one cardioversion attempt, and 3) subjects with 2 or more cardioversion attempts
- Length of in-hospital stay is defined as the number of hours from hospital admission to hospital discharge following cardioversion. The date and time of all hospital admissions and discharges following cardioversion will be captured within the CRF at Visit 2 and 3. Frequency of hospital stay, mean and median duration will be summarized by treatment arm.
 - Early cardioversion is defined as cardioversion that occurred within the first 7 days after randomization. Frequency and proportions will be reported by treatment arm.

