Appendix 1.3. Further Definition of Endpoints

N/A

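### The stroke definition requires a deficit of at least 24 hours and has no alternative for earlier death, so read literally it leaves a stroke fatal within 24 hours out of the stroke count and the stroke/systemic embolism composite

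*Protocol*

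**What the plan says.** Protocol 7.4.1 defines acute stroke as "a new, focal neurological deficit of sudden onset, lasting at least 24 hours" that has no readily identifiable non-vascular cause. Strokes are then classified into four types. The non-hemorrhagic type carries its own duration condition: a deficit from thrombus or embolus "that appears and is still partially evident at 24 hours". For the primary hemorrhagic type the section adds: "Evidence of hemorrhagic stroke obtained from lumbar puncture, neurosurgery, or autopsy can also confirm the diagnosis".

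Under Protocol 7.4 the investigator first judges whether an event satisfies the definitions: "Clinical events meeting the criteria will be recorded on the CRF and independently adjudicated". Protocol 9.4 has all clinical endpoints adjudicated blind to treatment, and says of the adjudicators: "The responsibilities and procedures followed are described in the Adjudication Charter". That charter is not among the documents.

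SAP 8.2.4 bases the stroke, systemic embolism and death analyses on adjudicated endpoints. One of its Kaplan-Meier displays is the "Composite of first adjudicated stroke or systemic embolism"; death is not a component of it. The SAP section headed "Appendix 1.3. Further Definition of Endpoints" is marked not applicable.

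**The concern.** A deficit cannot last 24 hours in a subject who dies sooner. Taken at its word, the definition excludes a stroke that kills at, say, 12 hours, and such strokes are among the most severe.

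The omission looks unintended. Fatal cases are provided for in the neighbouring definitions: major bleeding (Protocol 7.4.3) includes "Bleeding that is fatal", and systemic embolism (7.4.2) accepts autopsy evidence. Autopsy may also confirm hemorrhagic stroke within 7.4.1, so fatal strokes were evidently meant to count. Of these endpoints, only stroke has a minimum duration that an early death makes impossible to meet.

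At stake are the stroke rate, the stroke/systemic embolism curve and the risk ratio. The study is descriptive and expects only a handful of such events, so its results are essentially the event counts, and one classification decision is visible in them.

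**Working it through.** **Reading the text**

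1. The 24-hour condition is stated twice in Protocol 7.4.1, in the general definition and in the non-hemorrhagic subtype. Neither statement has an alternative for death.
2. The autopsy sentence sits under the primary hemorrhagic type. It settles the type of something already called a stroke and does not lift the duration condition above it.
3. The SAP supplies no further endpoint definition that could fill the gap.
4. What else would capture such an event:
   - Ischemic, fatal within 24 hours: all-cause death only. Systemic embolism does not apply, because 7.4.2 concerns peripheral arteries. No stroke-death or cause-specific death endpoint is listed in Protocol section 2 or SAP section 6.
   - Hemorrhagic, confirmed by imaging, fatal within 24 hours: all-cause death, and also major bleeding through the intracranial site or the fatal-bleeding criterion (7.4.3). Under SAP 8.2.4 bleeding is analysed in the Safety Analysis Set during treatment.

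**Inputs for the size**

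- About 1500 subjects randomized 1:1 (Protocol section 3), hence 750 per arm.
- Predicted stroke/systemic embolism events: 1 on apixaban and 3 on usual care, given as about 0.3% (Protocol 9.1).
- Share of these that are strokes fatal within 24 hours: not in the documents. Assumed range 5%, 10%, 25%.

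**The plan's own figure**

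(1 + 3) / 1500 = 0.267%, which rounds to the stated 0.3%.

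**If one event is not counted**

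The total becomes 3 / 1500 = 0.20%. With 750 in each arm the risk ratio equals the ratio of counts.

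| Counted events (apixaban vs usual care) | Total rate | Risk ratio | Fisher exact p |
|---|---|---|---|
| 1 vs 3 (as predicted) | 0.27% | 1/3 = 0.33 | 0.62 |
| 1 vs 2 (usual-care event lost) | 0.20% | 1/2 = 0.50 | 1.00 |
| 0 vs 3 (apixaban event lost) | 0.20% | 0/3 = 0 | 0.25 |

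**How likely that is**

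Expected loss = 4 × s, and probability of losing at least one = 1 − (1 − s)^4, where s is the assumed share. All 4 predicted events are treated as strokes, which overstates the loss because the figure includes systemic embolism.

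| Assumed share s | Expected loss | Probability of at least one |
|---|---|---|
| 5% | 0.2 | 19% |
| 10% | 0.4 | 34% |
| 25% | 1.0 | 68% |

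**The case against.** The strongest reply is that practice may already be right. The Adjudication Charter may classify early fatal strokes explicitly, and an adjudicator could read a deficit that persists until death as unresolved rather than as failing a duration test. This stands as a limit on certainty: the loss is what the text implies, not what is known to happen. It does not make the text sound, because an unwritten reading should not decide so sparse an endpoint.

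Several stronger conclusions that a reader might draw do not hold:

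- *That these events bypass blinded review.* All-cause death is itself a clinical endpoint and Protocol 9.4 covers all of them, so each case reaches the adjudicators as a death whatever the investigator decides about stroke. What remains open is the label they may give it.
- *That these events vanish from the study.* They stay in all-cause death, which has its own Kaplan-Meier display, and imaging-confirmed hemorrhagic cases also count as major bleeding.
- *That the curve is distorted by informative censoring.* The SAP states no censoring rule for the stroke/systemic embolism curve. Censoring at death would be the usual practice, but that is an inference, and it would affect every death. In the event-rate and risk-ratio summaries the subject stays in the denominator.
- *That a quarter of the events are lost.* 1/4 = 25% holds only if such an event occurs. Protocol 1.2 reports no stroke or systemic embolism within 30 days across 743 cardioversions in the earlier apixaban trial's sub-group, so the actual number may well be zero.
- *That one arm is favoured.* The definition is common to both arms, and losing one event can move the risk ratio either way.

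**Conclusion.** The point holds as a defect of wording with a small expected effect. Protocol 7.4.1 sets a 24-hour condition that a rapidly fatal stroke cannot meet, and nothing in the Protocol or SAP exempts such a case. Read literally, it is left out of the stroke count and the stroke/systemic embolism composite. The ischemic case is the more exposed, since only all-cause death records it.

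The expected loss is below one event for assumed shares under 25%, and the likely number is 0 or 1. One lost event would nevertheless be visible: 4 to 3 in total, and a risk ratio of 0.50 or 0 instead of 0.33. This rests on the Protocol's predicted counts, on an assumed share that the documents do not give, and on a charter that could not be checked. No directional bias is shown, and there is no hypothesis test or decision rule to be overturned.

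**What to change.** Add 'or resulting in death within 24 hours' to the general definition in Protocol 7.4.1, and extend the non-hemorrhagic subtype in the same way. Confirm that the Adjudication Charter says the same. Apply the rule to all events in both arms, including those already adjudicated, before database release.

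The cost is modest but not nil. Protocol section 9 requires a protocol amendment if the change counts as a major modification of an endpoint definition, and under section 12.1 an amendment needs ethics approval. Deaths already adjudicated must be checked for strokes fatal within 24 hours, still blind to treatment. Sample size, visits and treatment are unaffected.
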